5.2.7 Safety Analyses

5.2.7.1 Extent of Exposure

Extent of exposure will be described by the number of days of exposure (last date of dosing minus first day of dosing plus 1), and the number of days of exposure to each dose of the study drug (last date of dosing minus first date of dosing plus 1 summed over each period of time where the subject receives the same dose) will be summarized. No allowance will be made for breaks in therapy for the calculation of the total number of days of exposure. If the date of last dosing is completely missing, then the date of last dosing will be taken for analysis purposes as the date the relevant medication was last dispensed. If only the month of the last dose is recorded, the first day of the month will be assumed as the last dosing date.

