3 INVESTIGATIONAL PLAN

3.1 Overall Study Design and Plan

[figure not shown]
This is a multicenter, randomized, double-blind, placebo-controlled, 78-week, fixed-dose study evaluating AGB101 versus placebo as a treatment for slowing the progression of MCI due to AD.

The screening phase will occur 7 days to 42 days before the baseline visit (see Figure 4). After providing informed consent, subjects who meet entry criteria will be randomized 1:1 during the final baseline visit to receive either placebo or AGB101. A total of 160 subjects will be randomized (80/treatment group). Because of the PK and safety profile of AGB101, dosing will be initiated without titration and will be discontinued without tapering.

The baseline visit will occur 1 day before the study start. Subjects will be given their assigned study drug and instructed to take their 1st dose the next morning. A telephone contact will be made 1 week after the baseline visit to assess the subjects' medical status and inquire about any AEs/SAEs; similar telephone contacts will be made at weeks 17 and 56 with the same purpose. Study clinic visits are divided into minor visits ("clinic minor") at weeks 13, 39, and 65 and major visits ("clinic major") at weeks 26, 52, and 78. The difference between these two types of visits is the number and kinds of assessments performed. The "clinic minor" visits consist of a few basic assessments, while the "clinic major" visits consist of more in-depth testing, neuropsychological testing, and blood draws.

Subjects who enroll and subsequently discontinue the treatment before the 78-week visit will be followed up with a phone call at week 78 to assess their medical status and encourage them to come in to complete the early treatment termination/follow-up visit assessments.

Figure 4: Study Schema

Confidential Page 39 of 95

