- ⁶ 7 days after the baseline visit (week 1), day 119 (week 17), and day 392 (week 56), a phone call will be made to all the subjects to assess their medical status and inquire about any adverse events/serious adverse events.
- There will be approximately a 20 minute wait time between the immediate recall and delayed recall portion of the ISLT.
- The MMSE and the GDS will be administered, in this order, between the immediate recall and delayed recall portion of the ISLT.
- ⁹ A practice BPS-O will be administered at screening visit 1.
- MRI/PET scans may be redone if the scan is not technically satisfactory (as judged by the imaging vendor) within 2 weeks of the original scan as long as the radiation exposure is within the limits approved by the IRB.
- 11 Previous MRI scans will not be allowed. A baseline for structural imaging will be established using procedures in this protocol.
- 12 fMRI will only be performed as an optional procedure at JHU.
- Dosing begins the morning after the baseline visit.
- Prior medications will only be recorded during the screening phase (S1, S2, S3/B MRI).

Confidential Page 51 of 95

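### The imputation rules for a missing last-dose date have no lower bound, so the exposure summary can show zero or negative days for subjects who took drug

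*Combined protocol and SAP*

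**What the plan says.** Section 5.2.7.1 defines days of exposure as "last date of dosing minus first day of dosing plus 1". Interruptions are not subtracted: "No allowance will be made for breaks in therapy for the calculation of the total number of days of exposure". The figure therefore depends only on the two end dates.

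Two rules fill in the last date:

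- Date wholly missing: "the date of last dosing will be taken for analysis purposes as the date the relevant medication was last dispensed".
- Only the month known: "the first day of the month will be assumed as the last dosing date".

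Neither rule refers to the first dose date, the tablet count or the early-termination visit. I found no lower bound elsewhere in the document.

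The timing of the first dose matters here. In Section 3.1, "Subjects will be given their assigned study drug and instructed to take their 1st dose the next morning", and a footnote to Table 7 (Section 3.5.1) agrees: "Dosing begins the morning after the baseline visit". The first dispensing date is thus one day before the first dose date. Table 7 has further dispensing at weeks 13, 26, 39, 52 and 65, and none at week 78. Section 3.4.1 gives a 102-day supply each time. Section 5.2.1 limits the safety set to subjects with at least one dose, so true exposure in that set is at least 1 day.

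**The concern.** Both rules choose an early date, and nothing stops that date from falling before dosing began. Two ordinary situations then give a value that cannot be true. One is a subject lost after the baseline dispensing with no last-dose date. The other is a subject who stops in the calendar month of the first dose with only that month recorded. Such a subject belongs to the safety set and may have a treatment-emergent event, yet would appear in the exposure table with zero or negative days. Those values would enter the mean and could set the minimum.

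Outside these cases the rules still tend to shorten exposure, by up to about one dispensing interval. What is at stake is the accuracy of a planned safety summary.

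**Working it through.** The document states no exposure result to reproduce, so I first checked the formula against the planned duration and then applied each rule.

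**Inputs.** Exposure = last − first + 1 (Section 5.2.7.1). First dose = baseline + 1 day (Section 3.1). Week w visit = baseline + 7w days, ±5 days (Sections 3.5.2.4 and 3.5.2.5). Dispensing at baseline and weeks 13, 26, 39, 52 and 65 (Table 7). Supply 102 days (Section 3.4.1). Arm size 80 (Section 3.1).

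**Check with complete dates.** Dosing from baseline + 1 to baseline + 546 gives 546 − 1 + 1 = 546 days = 78 × 7, which matches the planned 78 weeks.

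**Date wholly missing (last dispensing date used).** If drug was last dispensed at week w, imputed exposure = 7w − 1 + 1 = 7w. If dosing in fact ran to the next scheduled visit, true exposure = 7(w + 13).

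| Last dispensed | Imputed days | Days if dosed to next visit | Shortfall |
|---|---|---|---|
| Baseline | 0 | 91 | 91 |
| Week 13 | 91 | 182 | 91 |
| Week 26 | 182 | 273 | 91 |
| Week 39 | 273 | 364 | 91 |
| Week 52 | 364 | 455 | 91 |
| Week 65 | 455 | 546 | 91 |

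- The baseline row is the impossible one: 0 days for someone who took drug.
- The week 65 row is a completer whose last-dose date was not recorded: 455 instead of 546 days, or 91/546 = 17% short.
- With both visits at the far ends of their windows, the interval is 91 + 5 + 5 = 101 days.
- If the subject stopped before the last dispensing and took none of that supply, the imputed date is too late and exposure is overstated.

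**Month only (first of the month used).**

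- Shortfall = (day of last dose) − 1, so 0 to 30 days. It is never negative, so this rule cannot overstate.
- In a 30-day month with the stop day uniform (an assumption), the mean shortfall is (0 + 1 + … + 29)/30 = 14.5 days.
- If first and last dose fall in the same month and the first dose is on day k, exposure = 1 − k + 1 = 2 − k. This is 1 at k = 1, 0 at k = 2 and negative from k = 3. The minimum is −28 in a 30-day month and −29 in a 31-day month.
- Example: first dose 10 March, last dose 25 March. Imputed: 2 − 10 = −8 days. True: 25 − 10 + 1 = 16 days.
- The rule can also place the last dose before a known dispensing. If week 65 drug is handed out on the 6th and the last dose is later that month, the imputed date is 5 days before dispensing: 455 − 5 = 450 days.

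**Effect on an arm mean.** The number of missing dates is not given, so these counts are assumptions. If 1, 4 or 8 of 80 subjects are completers with a wholly missing date, the arm mean falls by 91 × n/80 = 1.1, 4.6 or 9.1 days.

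**The case against.** Four points can be made for the plan.

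- **Missing dates should be few.** Section 3.3.3 requires a termination form for every dosed subject, Section 3.5.3 an early-termination visit as soon as possible, Section 3.4.6 return of containers at each visit, and Section 3.1 a call at week 1. This stands as a limit on frequency. The rules in Section 5.2.7.1, however, use none of these sources when a date is missing.
- **An earliest-date rule is a legitimate convention.** This stands for ordinary cases, where a lower bound on exposure is defensible if labelled as such. It does not excuse a value below 1 day for a dosed subject.
- **A floor is derivation detail.** Section 5.2 defers detail to an SAP to be signed before database lock, which may supply one. That is possible, but the rules as stated in the available document yield impossible values, so this is more than an omitted detail.
- **A later imputation can err as far the other way.** This also stands. Discontinued subjects are telephoned at week 78, so last contact may be long after the last dose. Someone who took few doses and returned no containers could be credited with about 102 days. The late date therefore belongs in a sensitivity summary, not in place of the main rule.

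A reader might also infer more than the document supports:

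- **That adverse event rates are distorted.** Section 5.2.7.2 plans subject counts and percentages, with no exposure-time denominator, so a subject with −8 days still counts once.
- **That other derivations inherit the error.** Treatment emergence depends on the first dose, period assignment on visit dates, and compliance on tablet counts. I found no other analysis using the imputed date.
- **That exposure is always understated, or only in early stoppers.** The dispensing-date rule can overstate, and completers with a missing date are affected too.

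**Conclusion.** The point holds and is minor. As written, the rules give 0 days to a subject dispensed only at baseline with no last-dose date, and 2 − k days to a subject who starts on day k and stops in that month with only the month recorded. Both results follow from the document's own formula and dispensing schedule, assuming the first dose is taken the morning after baseline as instructed.

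Beyond the impossible values, the month-only rule is short by 0 to 30 days; the average depends on the uniform-stop-day assumption. The dispensing-date rule is usually short, by up to about 91 days for visits on schedule and 101 within windows, but its direction is not certain. The effect is confined to the descriptive exposure summary; efficacy is untouched. The document does not allow an estimate of how many subjects are affected, or whether the arms would differ.

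**What to change.** Amend Section 5.2.7.1, or the SAP derivation, as follows:

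1. An imputed last-dose date may not precede the first dose date. For a month-only date, it also may not precede a dispensing date in that month when returned tablet counts show drug was taken from that supply.
2. Where a returned tablet count or an early-termination visit exists, use it to bound the date.
3. Report the number of imputed last-dose dates by arm.
4. Add a sensitivity summary using the latest plausible date: the earlier of month end, where the month is known, and end of supply.

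The floor moves the baseline-only case from 0 to 1 day and the March example from −8 to 1 day. It removes impossible values but not the shortfall, which is why item 4 is needed: month end gives 31 − 10 + 1 = 22 days in the March example, so 1 and 22 bracket the true 16.

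The cost is a few sentences and a little derivation code. The drawback is that the upper-bound summary may overstate exposure by up to one supply (102 days) for a subject with no tablet count, so it should be labelled as a bound. No dosing or visit procedure changes.

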5.2.7.2 Adverse Events

AEs will be summarized by treatment group and by maximum dose, latest dose received prior to the onset of the AE, by visit and treatment period.

A TEAE is defined as any AE that has an onset on or after the first dose of study drug, or any pre-existing condition that has worsened on or after the first dose of study drug, regardless of the causal relationship to the study drug. TEAEs will be attributed to a treatment using the following rules:

All analyses of AEs will be performed by the study period, so that it is possible to identify AEs that may be related to withdrawal from study treatment. The summaries of AEs will be limited to TEAEs. For summaries of TEAEs, a TEAE will be assigned to a given period if the date of onset of the TEAE is on or after the date of the first visit during the period but before the date of the first visit of the next period.

If the relationship of the AE to study drug is missing, it will be assumed to be related to the study drug for analysis purposes.

The incidence of subjects reporting TEAEs, treatment-emergent SAEs, TEAEs related to study treatment, treatment-emergent SAEs related to study treatment, and TEAEs leading

Confidential Page 73 of 95

to study discontinuation will be summarized using counts and percentages. The total number of TEAEs, treatment-emergent SAEs, TEAEs related to study treatment, treatment-emergent SAEs related to study treatment, and TEAEs leading to study discontinuation will also be summarized.

AEs will be coded using MedDRA. The incidence of TEAEs and treatment-emergent SAEs will be summarized at the subject level by MedDRA primary system organ class and preferred term using counts and percentages.

The incidence of TEAEs and treatment-related TEAEs will also be summarized by maximum severity and by closest relationship to study drug by MedDRA primary system organ class and preferred term. The summary will include the total number and percentage of subjects reporting a particular event. In counting the number of events reported, a continuous event, ie, an event reported more than once and which did not cease, will be counted only once; non-continuous TEAEs reported several times by the same subject will be counted as multiple events.

The incidence of TEAEs resulting in dose reduction will be summarized by the latest dose received and also by treatment group.

Withdrawal-related events will be tabulated separately.

Narratives of deaths, SAEs, and other significant AEs will be provided in the relevant section of the study report.

A complete subject listing of all AEs will be provided in the study report. This listing will include treatment, AE verbatim term, MedDRA primary system organ class and preferred term, the time of onset and cessation of the event relative to the first dose of study drug, duration of the AE, whether serious or not, severity, relationship to study drug, action taken, and outcome.

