3.5.3 Early Termination Visit and Early Termination/Follow-up Visit

Subjects who discontinue treatment (ie, at any time after randomization and before the week 78 visit) will have the early termination visit assessments performed as soon as possible after treatment termination. In addition, all subjects who enroll and subsequently discontinue will be followed up with a phone call during week 78 to assess medical status and encourage them to come in to complete the early termination/follow-up visit assessments.

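### In 5.2.7.2, visit-date periods and a TEAE definition with no end cannot by themselves separate on-treatment, withdrawal and late off-drug adverse events

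*Combined protocol and SAP*

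**What the plan says.** Section 5.2.7.2 (Adverse Events) contains four relevant statements.

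- **Definition.** "A TEAE is defined as any AE that has an onset on or after the first dose of study drug", extended to "any pre-existing condition that has worsened on or after the first dose of study drug, regardless of the causal relationship to the study drug". The start is first dose. No end is given.
- **Purpose.** AE analyses are done by study period "so that it is possible to identify AEs that may be related to withdrawal from study treatment".
- **Period rule.** "a TEAE will be assigned to a given period if the date of onset of the TEAE is on or after the date" of the period's first visit, "but before the date of the first visit of the next period".
- **Separate table.** "Withdrawal-related events will be tabulated separately". No selection rule or time window is attached.

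The section announces rules for attributing TEAEs to a treatment, but none of what follows is tied to last dose. It does not define study period either. The nearest thing to a definition is the set of column heads in Table 7: screening, baseline, treatment and early termination.

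Other sections bear on this. Under 3.5.3, subjects who stop early "will have the early termination visit assessments performed as soon as possible after treatment termination", with no maximum lag. Sections 3.3.3 and 3.5.3 seek follow-up to week 78, and 3.5.3.2 collects AEs at that visit. Section 3.4.2 says dosing stops without a taper. Section 5.2.7.1 uses the last dosing date, but only to compute exposure.

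**The concern.** The by-period analysis has a stated purpose, and the rule given for it does not serve that purpose. Withdrawal is defined by when dosing stopped, whereas the periods are defined by when visits took place. For a subject who stops early, the first days off drug come before the early-termination visit and so belong to the treatment period. Those are the days in which plasma levels fall to near zero, with no taper to spread the fall.

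At the other end, the definition never closes. An event many months after the last tablet is treatment-emergent on the same terms as one during dosing. Safety and tolerability against placebo is a stated objective (2.5). The reader of the safety tables should be able to tell which events arose on drug, which just after stopping, and which long afterwards.

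**Working it through.** The plan gives no figure on this point, so there is none to reproduce. The check has four steps.

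**1. What the period rule does under each reading of study period**

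| Onset in a subject who stops early | Early-termination visit opens a new period | It does not |
|---|---|---|
| Last dose to early-termination visit | Treatment | Treatment |
| Shortly after that visit | Early termination | Treatment |
| Months later, up to week 78 | Early termination | Treatment |

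Under the first reading, the early gap is filed under treatment, and the early-termination period mixes withdrawal events with remote off-drug events. Under the second, nothing is separated. On both readings every row is a TEAE.

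**2. How long the drug takes to leave**

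The half-life is 7.56 to 8.09 h (1.3). Section 1.5 reports an increase of 2.5 h in elderly subjects. Taking five half-lives as washout:

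- 5 × 7.56 = 37.8 h and 5 × 8.09 = 40.5 h, or 1.6 to 1.7 days.
- 5 × (7.56 + 2.5) = 50.3 h and 5 × (8.09 + 2.5) = 53.0 h, or 2.1 to 2.2 days.

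Unless the early-termination visit happens within about two days of the last dose, washout is complete before the period changes.

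**3. Share of withdrawal-window events filed under treatment**

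Let L be the days from last dose to the early-termination visit and W the length of the withdrawal window. Neither is in the documents, so both are assumed, with onset spread evenly over the window. The first reading in step 1 applies. The share is min(L, W) / W.

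| W | L = 1 | L = 3 | L = 7 | L = 14 |
|---|---|---|---|---|
| 7 days | 1/7 = 14% | 3/7 = 43% | 100% | 100% |
| 14 days | 1/14 = 7% | 3/14 = 21% | 7/14 = 50% | 100% |

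If withdrawal events cluster in the first days, the shares at short lags would be higher.

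**4. How far the open-ended definition reaches**

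Table 7 puts week 78 at day 546. Off-drug days that still count as treatment-emergent are 546 minus the day of last dose:

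| Last dose | Days |
|---|---|
| Week 13 (day 91) | 455 |
| Week 26 (day 182) | 364 |
| Week 52 (day 364) | 182 |
| Week 65 (day 455) | 91 |

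These are maxima. The plan promises a telephone call and encouragement to attend at week 78, not complete follow-up.

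**Completers.** Section 3.5.7 times the week 78 sample at 4 to 7 hours after a dose, so a completer's withdrawal interval falls after the last scheduled visit. Table 7 has no later period for them. What remains is 4.2.1, which covers events the investigator happens to detect within one month of the last scheduled visit and considers related or possibly related, and 4.2.2, which covers related SAEs found at any time after the study.

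**The case against.** The strongest reply is that the separate withdrawal table stands in its own sentence, and nothing says it must be built from the visit-date rule. AE onset dates and last-dose dates are both collected, so a correct table can be derived. That stands. A reader might infer that the promised table cannot be produced, but the documents support only that its rule is unspecified.

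Three further replies have force.

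- The early-termination visit is meant to be prompt. With a 1-day lag and a 7-day window, only 14% of window events are misfiled. It would be wrong to say that all withdrawal events are filed under treatment.
- If the early-termination visit opens a period, later off-drug events stay out of the treatment-period tables. The effect is then confined to overall TEAE summaries.
- Section 5.2 defers detail to a SAP to be finalized before database lock. It may supply the window, but no overriding AE rule appears in the documents reviewed.

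Other features of 5.2.7.2 do not rescue the rule. Summarizing by latest dose before onset cannot help, because there is one fixed dose. It treats an event a day after stopping and one a year later alike. The AE listing gives onset relative to first dose only.

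Two more stronger readings are tempting. One is that the withdrawal table will be empty for completers. Sections 4.2.1 and 4.2.2 allow some capture, so it will be incomplete rather than necessarily empty. The other is to turn off-drug follow-up into a percentage of person-time and call that the dilution of the AE comparison. The documents give no discontinuation rate for this trial, and the planned tables report subject counts, percentages and event totals. A person-time share would not measure bias in them.

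**Conclusion.** The point holds as a defect in a stated rule. The visit-date periods and the open-ended TEAE definition cannot by themselves achieve the separation that 5.2.7.2 says the by-period analysis is for, and the separate withdrawal table has no rule to make up for this.

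That conclusion rests on the text alone. The size does not: the misfiled share for a 7-day window runs from 14% to 100% as the lag goes from 1 day to 7 or more, and lag, window and even onset are all assumptions. The reach of the TEAE definition, such as up to 364 off-drug days for a subject stopping at week 26, follows from Table 7 but is an upper limit.

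The consequence is confined to safety tabulation. The primary and sequentially tested efficacy analyses are unaffected. The plan should be changed before unblinding, so that the windows are not chosen with the events in view.

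**What to change.** In 5.2.7.2, replace the visit-date rule with three intervals derived for every subject from dosing dates:

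1. **On-treatment:** first dose to last dose plus a short, pre-specified lag.
2. **Withdrawal:** a pre-specified window after last dose, following on from the lag without overlap.
3. **Off-treatment:** everything later.

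Use these intervals for the TEAE summaries and for the separate withdrawal table, and list off-treatment events separately. The sponsor should set the lag and window lengths and record the reasons.

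Flag every record with an imputed last-dose date. Section 5.2.7.1 substitutes the last dispensing date, or the first day of the month. Both tend to place the last dose early, which would move on-treatment events into the withdrawal interval.

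State in the SAP and the report that the withdrawal table is limited for completers, because collection after week 78 is passive. The one-month provision in 4.2.1 should not be used as an equivalent window. It runs from the last scheduled visit rather than last dose, and it takes only events judged related or possibly related, whereas events in subjects who stop early are collected regardless of cause.

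The cost is SAP wording and a small amount of extra derivation from dates already in the database. No new visit, contact or data item is needed.
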